- (3) Patients who should undergo other long-term merger resection during distal gastrectomy. (except cholecystectomy)
- (4) Patients with significant ascites by CT.
- (5) Patients with cirrhosis in CT brfore surgery
- (6) Patients with heart disease (history of uncontrolled hypertension, angina or coronary artery disease, history of cardiac muscle disease, Ejection Fraction <50%)
- (7) Patients with inappropriate renal function (serum creatinine > 1.4 mg/dL or BUN > 26 mg/dL)
- (8) Patients with abnormal coagulation (PT INR > 1.2 or aPTT > 45 sec)
- (9) Uncontrolled diabetic patients
- (10) Inflammatory bowel disease patients including Crohn's disease, ulcerative colitis, tuberculous enteritis
- (11) Patients taking aspirin or platelet inhibitors within 5 days before surgery
- (12) Patients taking anticoagulants

- (13) Patients with the history of steroid use which needs stress dose inoculation
- (14) Pregnancy
- (15) Other patients who are deemed unable to participate in the clinical trial by the tester
- (16) History of sensitivity to iodine, in case the test using indocyanine green is applied
- (17) Previous history of gout

3) Target number of subjects and basis of calculation

Total target number: 189, competitive enrollment at SNUH and SNUBH Calculation methods of the subjects

Primary evaluation variable: Cerum CRP value on Post-op 2nd day **Subjects of the study**

Main analysis group

- A. Ultrasonic shears
- B. Bipolar sealing device

Explorative analysis group

C. Hybride device

Study hypothesis:

- Null hypothesis: No difference in CRP value on post-op 2nd day between two groups.
- Alternative hypothesis: Difference in CRP value on post-op 2nd day between two groups.

Hypothesis for calculation of number of subjects:

- (1) Level of significance, $\alpha = 0.05$
- (2) Ratio between groups, group A: group B = 1:1
- (3) Type 2 error (β) is 0.20, retaining power of the test at 80%
- (4) Ultrasound dissector and Bipolar's post-op's CRP average and standard deviation was 11.5 ± 6.6 and 8.0 ± 2.8 from preceding research of "Research of availability and safety in using Articulating bipolar vessel sealer system in early Robotic gastrectomy in early stage gastric cancer". Subjected patients were 17, small in numbers and it was for Robotic LAP surgery, not conventional LAP surgery. Therefore, to avoid chances for reflecting not enough subjected patients, we have calculated subjected patient numbers from conservative standard deviation.

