Program used for calculation: PASS (Power Analysis and sample size software; http://www.ncss.com)

Calculation result of study subject number:

Croup	Gro	up 1	Group 2		Subject	Total subject	
Group Comparison Me	Maan	Standard	Maan	Standard	number of	number with 10%	
Companson	Mean	deviation	Mean	deviation	each group	omission rate	
A vs B	11.5	6.6	8.0	6.6	57	189	

^{*} Total subject number with 10% omission rate = subject number of each group / 0.9 * 3

The primary concern of this study is to compare ultrasonic shears (A) and advanced bipolar Sealing device (B). Hybrid instrument (C) is expected to have similar temperature from its operating features even though there is no previous trustworthy research. We have decided total of 189 target patients, same numbers in A and B in order to contrast balance weigh in equal condition.

4) Study subjects invitation plan

Invitation will be made to patients, satisfying selection/exemption criteria among those who are gastric cancer patient visiting Gastric Cancer Center in Seoul National University Hospital or hospitalized gastric cancer patient who requested gastric cancer treatment to the study research team. Invitation will be explained verbally, with a consent form.

11. Research method

1) Research method in detail

Under general anesthesia of the patient, satisfying selection/exemption criteria, the subject will be appointed to the each study group of 1:1:1 ratio and the surgery will only use an energy-based device of each selected group. The patients will be randomized using web-based program, which will be generated by medical research collaboration center (MRCC), Seoul National University Hospital. Institutes and the presence of incision during anastomosis (intracorporeal or extracorporeal anastomosis) will be the stratification factors during randomization. Blood loss, blood transfusion volume, operation time, cytokines and others will be measured during the operation and amount of drainage, laboratory test and adverse reaction will be post-operatively observed and accessed. Unless follow-up or extension of admission is needed due to the adverse reaction, patients will be discharged during the post-op 5-10 days. Follow-up will be made until the first out-patient visit after 2-3 weeks of discharge.

(1) Evaluation criteria during operation

① Blood loss during operation: Output-input.

The blood loss will be measured with sum of absorbed blood in gauzes and absorbed amount using inhalator.

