- After the screening number was assigned, the subjects who satisfied all the inclusion criteria and were not eligible for any exclusion criterion were judged to be suitable for the study. After the insertion of the laparoscopic trocar under general anesthesia, (Eg, after a confirmation of unexpected intraperitoneal or severe adherence do not exist), randomization should be performed. A randomization number (patient ID) will be awarded in a strictly sequential manner in accordance with the randomization table generated by the medical statisticians in advance.
- The randomized method uses a centralized stratified block randomization method to ensure a balanced distribution among the three groups. Institutes and the presence of incision during anastomosis (intracorporeal or extracorporeal anastomosis) will be the stratification factors.
- If a clinical trial subject discontinues clinical trials, the random assignment number assigned to the subject will not be re-used and the subject will not be able to participate in the trial again.
- The trial will be conducted with a single blind spot. Therefore, the practitioner knows the contents of the randomization, but does not disclose the contents of the clinical trial subjects for about 4 weeks after the end of the clinical study.

3) How to use test medical device, combination therapy, reasons for selection when using treatments

Energy-based devices are used in accordance with the manufacturer's manual and the commonly used principles of laparoscopic surgery, and the sites of use during surgery are as described in above 9-1)-(2).

4) Observation items, clinical examination items and observational examination methods

- (1) Primary endpoint: Serum C-reactive protein (CRP) at POD 2
- (2) Secondary endpoint:
 - Blood loss during operation, amount of blood transfusion

- IL-6, IL-10 in serum and ascites at 2-3 hours after surgery and POD 2, 4
- Complication within 30 days after surgery, mortality rate
- At 4 days postoperatively, serum CRP
- Postoperative visual pain score (VAS score)
- The timing of gas release after surgery, start time of liquid diet
- Length of stay, re-admission, emergency room visit and reasons
- Amount of drainage after surgery
- Concentration of triglyceride and amylase in drain
- Amount of Indocyanine green in the peritoneal cavity after surgery, which is injected submucosally before dissection (only in Seoul National University Hospital)
- Number of resected lymph nodes

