- 16) Endocrine: Diabetic ketoacidosis, hyperglycemic hyperosmolar state, Addison's disease, hypothyroidism, etc. Clinically diagnosed
- 17) Stasis: Refers to the case where food is obstructed to pass through the anastomosis, even though there is no evidence of intestinal obstruction, stenosis, leakage, or peritonitis.

- 18) Pancreatic leakage: A case when the amylase level of the drain tube 3 days or more after surgery exceeds 540 U/L, which is three times the normal maximum value of 180 U/L of the normal blood test (1, 3, Check on day 5).
- 19) Chylous ascites: Suspected when the color of a clear white fluid is found with the naked eye, and JP diagnoses that triglyceride is 110 mg/dL.
- 20) Deep Vein Thrombosis
- 21) Central venous infections

9) Evaluation standards, evaluation methods and analysis methods (statistical analysis methods, etc.)

- (1) Primary endpoint: Two days after surgery, serum CRP
- ; Student's t test or ANOVA test was performed by using the mean of CRP value on the second day between the three groups.
- (2) Secondary endpoint:
- Blood loss during operation (ml), amount of blood transfusion (pint); Output-input (ml). Gauze measures the total weight of gauze used during surgery and calculates the difference from the gauze weight measured before surgery. Inhalation volume is calculated by subtracting the amount of 0.9% physiological saline solution applied to the surgical site from the total inhalation volume.
- Serum IL-6, IL-10

Serum IL-6 and IL-10 levels were measured at baseline immediately after general anesthesia and insertion of the trocar. The mean value of serum IL-6 and IL-10 levels 2-3 hours after the operation, the 2nd postoperative day, and the 4th postoperative day are compared by Student's t test or ANOVA test.

- Amount of remaining ICG: Total amount of the remaining ICG will be calculated by the mean value of concentration of the ICG measuring 3 sets for each patient multiplied by 500 (ml) (600 or 700 ml for corresponding cases), and the mean value of the amount of ICG will be compared between each group using t test.

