- Complications and mortality rate within 30 days after surgery: Clavien-Dindo classification is used to grade the complications of the three groups and the $\chi 2$ test is performed using the Cross Table for the frequency of complications and Grade IIIa complications. For the total complications, the Student's t test or the ANOVA test was performed using the Comprehensive Comorbidity Index between the three groups.

- After 4 days postoperatively, serum CRP, amylase, serum/ascites triglyceride: The preoperative mean value was used as the baseline and the Student's t test or the ANOVA test was performed on the mean value of the three groups at the 4th postoperative day
- Post-operative pain medication frequency: Student's t test or ANOVA test is performed on the average daily frequency of use among the three groups of non-PCA narcotic analgesics.
- Postoperative visual pain score (VAS score): The mean postoperative VAS score between the three groups is verified by Student's t test or ANOVA test.
- Post-operative transfusion, gas evacuation, liquid diet initiation: If the postoperative Hb < 8, transfusion can be performed under the judgment of the tester and record transfusion. The mean number of days from the day of surgery was verified by Student's t test or ANOVA test among the three groups.
- Length of hospital stay: The average number of days between surgery and discharge is assessed by Student's t test or ANOVA test among the three groups.
- Re-admission, emergency room visit: Within 30 days from the date of surgery, record admission / visit and evaluate complications if you are re-admitted to the hospital or visited the emergency room.
- A new version of the harmonic scalpel was introduced during the research and the target of the ultrasonic group is being studied with a new product. (Since IRB approval in July 2018)
- We will compare the results of the patients who underwent surgery in the ultrasonic group regarding to old instrument versus new instrument. In the comparison between the groups, it will be analyzed whether there is a difference between the inclusion and the non-inclusion of the subject who underwent surgery with the old apparatus. In these ways, it will be notated in the final report whether there is any influence on the results of the study by the change of the device.

9-1) General principles of statistical analysis.

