A multivariable analysis of primary and primary secondary efficacy variables is performed. Multivariate analysis uses multiple linear regression models or multiple logistic regression models depending on the type of outcome variable. The main independent variable is the test, we will include the gender and stage of the stratified variables used in randomization in the model and the perturbed variables identified in the demographic and clinical history data analyzes to control the effect. For repeated measurement data, perform a multivariate analysis using the generalized estimation equation (GEE). If a significant interaction effect is found between the treatment group and the participating laboratories and / or the treatment group and the confounding variables, the effect is controlled by including the interaction term in the multivariate model.

• The content of the pre-planned subgroup analysis to be performed in this trial is as follows:

- Gender Male Female)
- BMI (<25 / ≥25)
- Cancer stage (TNM stage)
- Operator
- In vitro / Internal Anastomosis
- The differences between the groups were assessed using the Student's t-test (or the corresponding nonparametric Wilcoxon rank-sum test) or the χ2 test (or Fisher's exact test, the corresponding nonparametric method) Analysis. If control of disturbance variables is required, multivariate analysis is performed.

9-2) Treatment of missing values.

In general, the missing value will be treated as a missing state, and no alternative missing statistic is used. Therefore, only observations will be used for data analysis. Discrepancies data are replaced by missing values at the responsibility of the clinical trial manager.

10) Clinical trial and treatment standard

The same type of treatment and treatment will be given to patients with general gastric cancer who are being treated at Seoul National University Hospital.

11) Study Schedule

- 42 months after IRB approval: registration of clinical trial subjects and clinical trials
- 42 months ~ 48 months: Data analysis and presentation

12. Data and Safety Monitoring Plan

1) The person in charge of monitoring

- * Monitoring supervisor: [name], Associate Professor, Surgery, Seoul National University Hospital
- * Person in charge of monitoring: [name], Department of Nurse, Seoul National University Hospital

2) Data and safety information monitoring items

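### The multivariable model calls gender and stage the randomisation strata, but randomisation is stratified by institute and anastomosis type, and no analysis prespecifies those two as covariates

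*Combined protocol and SAP*

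**What the plan says.** The stratification factors are given twice, in agreement. Section 11-1), Research method in detail: "Institutes and the presence of incision during anastomosis (intracorporeal or extracorporeal anastomosis) will be the stratification factors during randomization". Section 11-2), on random assignment, describes central stratified block randomisation and repeats: "Institutes and the presence of incision during anastomosis (intracorporeal or extracorporeal anastomosis) will be the stratification factors". It places randomisation "After the insertion of the laparoscopic trocar under general anesthesia", once unexpected intraperitoneal findings or severe adhesions have been ruled out.

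The multivariable analysis under 9-1) names different factors: "we will include the gender and stage of the stratified variables used in randomization in the model". It adds confounders to be identified later from the demographic and clinical history data.

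The primary analysis in section 11-9) (1) has no covariates: "Student's t test or ANOVA test was performed by using the mean of CRP value on the second day between the three groups".

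The true strata appear in the analysis text in two other places, both under 9-1). Anastomosis type is one of the planned subgroups. The participating sites (the translation says laboratories) may enter through an interaction with treatment, but only if that interaction is significant. The same section promises a separate SAP before database lock.

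**The concern.** The sentence under 9-1) evidently means to adjust for the variables used in randomisation, yet it names two that were not used and omits the two that were. An analyst who follows its wording fits gender and stage. An analyst who follows its stated purpose fits institute and anastomosis type. Both could claim to have followed the plan for a model of the primary outcome.

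There is also a question of precision. Stratified blocks balance the arms on the strata. If the strata predict CRP, the difference in means varies less between trials than the ordinary t-test standard error implies. An unadjusted test then gives no credit for that balance: its type I error falls below 5% and some power is forgone. What has to be settled is how large that loss is, and whether the validity of the primary result is affected.

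**Working it through.** **1. The passages side by side.**

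| Place | Factors | Role |
|---|---|---|
| 11-1) | institute, anastomosis type | randomisation strata |
| 11-2) | institute, anastomosis type | randomisation strata |
| 9-1), multivariable model | gender, stage | described as the randomisation strata |
| 9-1), subgroups | anastomosis type among others | subgroup only |
| 9-1), interaction rule | participating sites | only if the interaction is significant |
| 11-9) (1), primary test | none | unadjusted |

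No section stratifies randomisation by gender or stage, and none names institute or anastomosis type as a prespecified main effect.

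**2. The plan's sample size.** Inputs from section 10-3): means 11.5 and 8.0 (difference 3.5), SD 6.6 in both groups, alpha 0.05 (taken as two-sided, since the alternative is non-directional), power 80%, 10% omission. A two-sample t-test calculation gives 56.8, so 57 per group, with power 80.1%. Then 57 / 0.9 × 3 = 190, against 189 (3 × 63) in the plan, which is a rounding difference. Correcting the strata does not change this number.

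**3. Normal approximation.** Let R² be the share of CRP variance that the true strata explain (assumed; not in the documents), and let s = √(1 − R²). The standardised difference is 3.5 / (6.6 × √(2/57)) = 3.5 / 1.236 = 2.83.

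- Type I error, unadjusted: 2 × [1 − Φ(1.96 / s)]
- Power, unadjusted: Φ((2.83 − 1.96) / s)
- Power, adjusted for the strata: Φ(2.83 / s − 1.96)

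At R² = 10%, s = 0.949. Type I error is 3.9%, power 82.1% unadjusted and 84.7% adjusted.

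**4. Simulation.** 189 patients in three arms, permuted blocks within four strata, 9.5% missing at random (63 × 0.905 = 57.0 per arm), ultrasonic versus bipolar analysed, 12,000 runs per cell. The simulation standard error of a power near 80% is √(0.8 × 0.2 / 12,000) = 0.4 points. Assumed, because the documents do not give them: block size 6, institutes 60/40, anastomosis types 50/50, and R² split equally between the two factors.

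| R² assumed | CRP shift needed, institute / anastomosis | Power unadjusted | Power adjusted for true strata | Gain, points | Type I error unadjusted |
|---|---|---|---|---|---|
| 0% | 0 / 0 | 80.1% | 80.0% | 0 | 5.0% |
| 2% | 1.35 / 1.32 | 80.8% | 81.3% | 0.5 | 4.9% |
| 5% | 2.13 / 2.09 | 81.1% | 82.4% | 1.3 | 4.5% |
| 10% | 3.01 / 2.95 | 81.5% | 84.2% | 2.7 | 4.2% |
| 20% | 4.26 / 4.17 | 82.0% | 87.6% | 5.6 | 3.2% |

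The shifts follow from (R²/2) × 6.6² = p(1 − p) × shift². At 2% with p = 0.6, 0.4356 / 0.24 = 1.815, and its square root is 1.35. Type I error of the adjusted test stays between 5.0% and 5.1%.

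**5. Sensitivity.** At R² of 5, 10 and 20% the gain is 1.3, 2.7 and 5.7 points with block size 3; 1.5, 3.0 and 5.9 with block size 9; and 1.4, 2.9 and 5.7 with an 80/20 split of anastomosis type.

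Section 10-3) reports from the pilot "CRP average and standard deviation was 11.5 ± 6.6 and 8.0 ± 2.8". With those SDs (pooled √((6.6² + 2.8²)/2) = 5.07), unadjusted power runs from 95.3% to 96.9% over the same R² values. The gain is about 0, 0.1, 0.3, 0.9 and 1.4 points.

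**The case against.** The error sits in a supportive model, and the primary test is sound without it. Adjusting for gender and stage is legitimate in itself, because a baseline covariate need not be a stratification factor. If gender predicted CRP better than the strata do, that model would be the more powerful one: in a simulation of 3,000 runs with gender assumed to explain 10% and the strata 2%, power was 84.0% with gender and stage and 81.3% with the strata. The sentence is badly translated, so a lost conjunction is plausible, and a SAP is still to come. Finally, changing a primary analysis late in a trial whose operators know the allocation raises its own credibility question, for a gain that may be close to nil.

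Most of this stands as a limit on the size of the concern. It shows that there is no threat to validity, that the wording under 9-1) cannot be assigned a power cost, and that moving to an adjusted primary analysis brings a modest benefit. It does not remove the contradiction. A translation slip in an operative analysis rule still has to be corrected, and a SAP drafted from that sentence would inherit it.

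Section 11, 4-2) puts randomisation before surgery, whereas 11-2) puts it after trocar insertion. Either way it precedes the anastomosis, so the advice to use the value entered at randomisation is unaffected.

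**Conclusion.** The concern holds, and it is minor. The plan misstates its own stratification factors, and no analysis prespecifies institute or anastomosis type as a covariate. The primary test of day 2 CRP is valid, has about 80% power under the design assumptions, and produces no extra false positives. If the strata do not predict CRP, nothing is lost. If they explain up to 5% of its variance, adjustment would gain at most about 1.3 points of power at SD 6.6 under the main assumptions. Gains of 2.7 and 5.6 points require each factor to shift CRP by about 3.0 or 4.2, against a design difference of 3.5, and nothing in the documents supports effects of that size. These figures rest on the assumed R², block size and stratum proportions. The textual contradiction rests on none of them.

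**What to change.** **Needed.** Under 9-1), name institute and anastomosis type as the stratification factors in the multivariable model, using the values entered at randomisation. Gender and stage may remain as prognostic covariates, labelled as such. If the Korean text meant gender and stage together with the strata, say so. This is a wording change.

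**Recommended.** In the SAP, prespecify the ultrasonic versus bipolar comparison of day 2 CRP as a linear model on device, institute and anastomosis type, with the unadjusted t test as a sensitivity analysis. The rank-sum fallback under 9-1) can stay. The two strata cost 2 degrees of freedom. No new data are needed, because both factors are recorded for randomisation.

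This second step amends the primary analysis. It must be documented and dated before database lock and before any look at outcomes by arm. The caution is necessary because patients were already being treated before version 2.1 of July 2021 (section 11-9) notes "A new version of the harmonic scalpel was introduced during the research", with approval in July 2018) and because, under 11-2), "the practitioner knows the contents of the randomization". If the sponsor prefers to keep the unadjusted test as primary, the correction under 9-1) is still required.

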A Statistical Analysis Plan (SAP) will be created before the database locks. A blinding review of the data will focus primarily on issues related to the exclusion of patient or patient data from missing and analyzed data.

The subjects to be validated for the data obtained from the subjects of the clinical trial are

classified into the ITT (intention-to-treat) analysis group and the PP (per protocol) analysis target group.

- ITT analysis group consisted of all randomized subjects after satisfying the selection / exclusion criteria.
- The subjects who underwent the PP analysis were those who completed the clinical trials of the ITT target group, and observed the primary efficacy variables as planned without violating the critical clinical trial plan. Completion of the clinical trial is defined as discharge following normal procedure without further hospitalization after surgery. Critical clinical trial protocol violations include:
 - · Violation of selection / exclusion criteria
 - · Random assignment violations
 - Take medication for concomitant medication
 - In case of any other serious clinical trial protocol violation
- The analysis of the basic characteristics of the patients, including demographic data and clinical history data, is evaluated using the ITT analysis group. All of the validation variables were analyzed for the ITT group and the PP group. The results of the study on serum CRP at day 2 postoperatively were used as the main evaluation group.

Safe Safety evaluation variables such as adverse events and adverse reactions are analyzed using the safety analysis target group.

- The safety analysis group consisted of all subjects who underwent randomized placement.
- Statistical tests for all efficacy / safety parameters should be performed at the 5% significance level. If the data do not meet the assumptions needed to perform a parametric test, a non-parametric test such as the Wilcoson rank-sum test is performed.

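### The adjusted analysis of POD 2 CRP takes its extra covariates from the trial's own data and misnames the randomisation strata; the covariate list should be fixed before database lock

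*Combined protocol and SAP*

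**What the plan says.** The primary endpoint section (section 11, 9)(1)) gives an unadjusted comparison: "Student's t test or ANOVA test was performed by using the mean of CRP value on the second day between the three groups".

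Section 11, 9-1) then adds a second analysis of the same endpoint: "A multivariable analysis of primary and primary secondary efficacy variables is performed". Its covariates come from two sources:

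- Named in advance: "we will include the gender and stage of the stratified variables used in randomization in the model".
- Not named in advance: "the perturbed variables identified in the demographic and clinical history data analyzes". The wording is evidently a translation of confounding variables, the term used later in the same paragraph. No candidate list, test, threshold or deadline follows.

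If an interaction of treatment with centre or with a confounder proves significant, "the effect is controlled by including the interaction term in the multivariate model".

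On the strata, section 11, 1) reads: "Institutes and the presence of incision during anastomosis (intracorporeal or extracorporeal anastomosis) will be the stratification factors during randomization". Section 11, 2) names the same two factors.

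The schedule of examinations in section 11, 4) has CRP measured again within 2 days before surgery. Section 9-1) promises a SAP before database lock but does not say that it will settle the covariates. The blinded data review described there is directed mainly at exclusions and missing data.

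**The concern.** In a randomised trial, covariates are best chosen before the data are seen, for their expected relation to the outcome and because they were used to stratify. Here the additional covariates are settled by looking at the trial's own baseline data: "The analysis of the basic characteristics of the patients, including demographic data and clinical history data, is evaluated using the ITT analysis group". Two analysts following this text could fit different models to POD 2 CRP and report different adjusted p values, each within the plan.

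The part that is fixed in advance does not repair this, because it rests on a mistaken description of the strata. Institute and anastomosis type are not listed as covariates. Centre appears in that paragraph only through a possible interaction term, and anastomosis type only as a subgroup factor. If either factor is prognostic, leaving it out of the model discards the precision that stratification was meant to secure.

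At stake is the credibility and efficiency of the adjusted A (ultrasonic) versus B (bipolar) result. The plan does not rank that result below the t test, and section 9-1) applies the 5% level to all efficacy tests.

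**Working it through.** **1. The passages side by side**

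| Item | Randomisation (section 11, 1) and 2)) | Adjusted model (section 11, 9-1)) |
|---|---|---|
| Institute | Stratification factor | Not named as a covariate |
| Intra-/extracorporeal anastomosis | Stratification factor | Not named as a covariate |
| Gender, stage | Not stratification factors | Included, described as strata |
| Pre-operative CRP | Not a stratification factor; measured within 2 days before surgery | Not named |
| Other covariates | – | Chosen from the trial's demographic and clinical-history data |

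The two descriptions of the strata cannot both be right, and nothing elsewhere reconciles them.

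**2. The plan's own figure**

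Inputs from section 10, 3): means 11.5 and 8.0 (difference 3.5), SD 6.6 in both groups, alpha 0.05, power 80%. The test is taken as two-sided because the alternative hypothesis is non-directional.

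- Normal approximation: n = 2(1.960 + 0.842)² × 6.6² / 3.5² = 55.8, so 56 per group.
- Two-sample t test: 56.8, so 57 per group as stated, with power 80.1%.
- Total: 57 / 0.9 × 3 = 190, against 189 stated (63.3 per group taken as 63). The figure reproduces to within rounding.

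The calculation contains no covariate adjustment, so its 80% does not rest on the multivariable model.

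**3. What one fixed covariate could add**

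The documents give no correlation ρ between any baseline variable and POD 2 CRP, so ρ is an assumption. Residual SD = 6.6 × √(1 − ρ²); standard error = residual SD × √(2/57). Power is from the t test at 57 per arm.

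| Assumed ρ | Residual SD | Standard error | 3.5 / standard error | Power |
|---|---|---|---|---|
| 0 | 6.60 | 1.236 | 2.83 | 80.1% |
| 0.1 | 6.57 | 1.230 | 2.85 | 80.5% |
| 0.2 | 6.47 | 1.211 | 2.89 | 81.7% |
| 0.3 | 6.30 | 1.179 | 2.97 | 83.7% |
| 0.5 | 5.72 | 1.071 | 3.27 | 90.0% |

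**4. How far pre-operative CRP can go**

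Section 10, 1)(7) admits only patients with CRP of 1.0 mg/dl or less. A variable confined to 0–1.0 has an SD of at most 0.5. Assuming POD 2 CRP is in the same units, the slope needed is ρ × 6.6 / SD:

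- ρ = 0.5: at least 0.5 × 6.6 / 0.5 = 6.6 mg/dl per 1 mg/dl, nearly twice the 3.5 treatment difference.
- ρ = 0.3: at least 0.3 × 6.6 / 0.5 = 4.0 mg/dl per 1 mg/dl.

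The 0.5 row is therefore implausible for CRP, and even 0.3 may be generous.

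**5. Does the open rule inflate type I error?**

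Simulation under no difference: 57 per arm, 8 independent baseline variables, 2 of them prognostic with joint R² of 0.1 to 0.3 (assumed), 6,000 runs for each R².

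| How the model is chosen | Type I error |
|---|---|
| Rigid rule: adjust for variables with baseline p < 0.05 | 4.2–4.9% |
| Better of the unadjusted and the rigid-rule result | 5.5–5.8% |
| Free search, up to 2 of the 8 variables | 9.7–11.5% |

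Only the free search inflates the error materially, and the plan does not describe one.

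**The case against.** The strongest reply is that the primary test is unadjusted, the sample size was set without adjustment, and the multivariable model is an additional analysis. That stands: if the t test or ANOVA is kept as primary, its p value and its 80% power are untouched. It is not a complete answer, because the plan specifies the model for the primary endpoint and never calls it supportive.

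Several stronger readings are tempting, and the documents do not support them:

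- **A baseline significance screen.** A reader might infer that covariates enter when they differ between arms at 5%. The text gives no test or threshold, and a confounder could equally be identified by its link to outcome. A rigid screen of that kind would not inflate type I error in any case.
- **A badly inflated type I error.** A free search over all 32 subsets of five covariates gives about 12% at correlations of 0.2 and 17% at 0.3. That is a worst case under deliberate searching. Five independent covariates at 0.3 also imply a joint R² of 5 × 0.09 = 0.45.
- **Power of 90% forgone.** This needs a correlation of 0.5, implausible for CRP under the entry limit.
- **Adjustment only if judged necessary.** The sentence "If control of disturbance variables is required, multivariate analysis is performed" follows the subgroup list. The multivariable analysis of the primary endpoint is planned unconditionally.

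The promised SAP could close the gap, but nothing in the documents commits it to doing so.

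**Conclusion.** The point holds for the adjusted analysis only. Its additional covariates are left to be identified from the trial's own data, its named covariates are wrongly described as the strata, and the actual strata and pre-operative CRP are not named. The adjusted A versus B result is therefore open to analyst choice and may be less precise than it could be.

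The size is modest. On the plan's 3.5 difference and SD of 6.6, one fixed covariate with an assumed correlation of 0.1 to 0.3 lifts power from about 80% to between 80.5% and 84%; pre-operative CRP may well give less than the upper figure. The planned 57 per group and 189 in total need no change. This is a low-cost improvement, not a threat to the primary test.

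**What to change.** In the SAP to be written before database lock:

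1. Replace the data-driven selection with a fixed list: institute and anastomosis type as entered at randomisation, and pre-operative CRP. Gender and stage may stay if they are wanted as prognostic covariates, but should no longer be described as strata.
2. State which analysis of POD 2 CRP is primary, the unadjusted comparison or the adjusted model.
3. Label any covariate added later as a sensitivity analysis.

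Database lock is the practical deadline: the trial is single-blind and the practitioner knows the allocation, so a deadline tied to unblinding would have little force.

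The cost is SAP wording; the listed variables are already collected. The one small drawback is that a chance imbalance in an unlisted variable would be handled only in a sensitivity analysis.
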